8.2. Pharmacodynamic Assessments

The following PD assessment will be determined with the blood samples collected. Data may be normalized to pre-dose samples and expressed as % of pre-treatment or the values measured may be used.

9.0 ASSESSMENT OF SAFETY

9.1. Safety Parameters

Safety and tolerability will be determined by change from baseline in symptoms, signs, and laboratory tests, by elicitation of AEs (Section 9.2) and by concomitant medication usage (Section 5.2). All events will be followed until resolution and appropriately reported on the AE Case Report Form. Laboratory abnormalities should be reported as AEs if clinically significant per the Principal Investigator (Section 9.2.5.3).

9.1.1. Demographic/Medical History

A medical history, including demographics (i.e., age, race, sex) and concomitant medication usage will be obtained at the screening visit.

9.1.2. Physical Examination

9.1.2.1. Complete Physical Examination

A complete physical examination (PE) will be conducted at the screening visit and Day -1; this consists of measurements/examination of the following:

- Weight
- Height
- Eyes
- Ears, Nose, Mouth, Throat
- Neck
- Respiratory
- Cardiovascular
- Chest (Breasts)
- Gastrointestinal (Abdomen)
- Genitourinary (to be performed at the discretion of the Principal Investigator to follow-up on any relevant medical history e.g., menstrual bleeding)
- Lymphatic
- Musculoskeletal
- Skin
- Neurologic

9.1.2.2. Brief Physical Examination

A brief PE will be conducted 24 hours post dose (i.e., on Day 2) and 120 hours post dose (i.e., on Day 6). The brief physical examination will consist of measurements/examination of the following:

- Weight
- Eyes
- Ears, Nose, Mouth, Throat
- Neck
- Respiratory
- Cardiovascular

9.1.3. Vital Signs and Body Temperature

Vital signs (heart rate, blood pressure, respiratory rate) will be measured pre-dose (\leq 30 minutes before dosing) and at the time points specified in the Table 5, *Schedule of Assessments*, after the patient has been in the sitting position for at least 5 minutes. Body temperature will be measured in degrees Celsius (°C).

9.1.4. Weight and Height

Weight will measured at the screening visit, Day -1, 24 hours post dose (i.e., on Day 2) and 120 hours post dose (i.e., on Day 6, at the study termination visit) and will be recorded in kilograms.

Height will be measured at the screening visit only and will be recorded in centimeters. (See Table 5, *Schedule of Assessments*.)

9.1.5. Electrocardiogram

Each patient will undergo a standard 12-lead ECG at baseline at the screening visit, 3.0 hours post dose, and 24 hours post dose. The ECG will be obtained after the patient is in the supine position for at least 5 minutes (optimally 10 minutes).

9.1.6. Routine Clinical Laboratory Assessments

In Part 1 of the study, a total of approximately 53 to 63 mL of blood (depending on Cohort) will be drawn from each patient over a period of approximately 5 weeks. Approximately 2 mL will be drawn for each PK sample, 4.5 mL for each PD sample, and approximately 5 mL for hematology, coagulation, and chemistry samples, per local institution requirements. Urinalysis will also be performed. To minimize pain and discomfort to pediatric subjects during the blood sampling time points, sampling may occur via IV catheter or butterfly needle followed by saline flush. For patients with pre-existing central venous catheter or CVAD (i.e., central line, central venous line, or central venous access catheter) sampling may occur via these access points.

This protocol will be amended prior to the commencement of Part 2, and again prior to the commencement of Part 3 to specify age appropriate blood sampling volumes and time points. Part 2 and Part 3 of the study will only commence upon written approval of an amendment to this protocol by applicable regulatory bodies (i.e., IEC/IRB, MOH, and CA, as appropriate).

9.1.6.1. Hematology

Hematology assessments comprise a Complete Blood Count (CBC) and coagulation panel, as specified below:

- **CBC:** Absolute Neutrophil Count (ANC), basophils, differential, eosinophils, Hematocrit (HCT), Hemoglobin (Hgb), lymphocytes, Mean Corpuscular Hemoglobin (MCH), Mean Corpuscular Hemoglobin Concentration (MCHC), Mean Corpuscular Volume (MCV), monocytes, neutrophils, platelet count, Red Blood Cell (RBC) count, Red cell Distribution Width (RDW), reticulocyte, and White Blood Cell (WBC) count relative and absolute.
- **Coagulation Panel:** Activated Partial Thromboplastin Time (aPTT), Pro-Thrombin and International Normalized Ratio (PT/INR).

9.1.6.2. Blood Chemistry

Blood chemistry analyses comprise a complete blood chemistry analysis and, if applicable, analysis of Gamma-Glutamyl Transpeptidase (GGT), as specified below:

• Complete Blood Chemistry Analysis: Alanine transaminase, albumin, Alkaline Phosphatase (ALK/ALP/ALKP), Aspartate Aminotransferase (AST), bilirubin (total), Blood Urea Nitrogen (BUN), calcium (Ca), chloride (Cl), creatinine, glucose, Lactate Dehydrogenase (LDH), potassium (K), SGOT (AST), SGPT (ALT), sodium (Na), uric acid, GGT.

9.1.6.3. Urinalysis

Obtain urine samples at protocol-specified time points (Table 5, *Schedule of Assessments*) for a complete urinalysis and microscopic urinalysis, if applicable.

- **Complete Urinalysis:** Bilirubin, blood, color, glucose, ketone/acetone, leukocytes, nitrite, pH, protein, specific gravity, turbidity (clarity), urobilinogen.
- **Microscopic Urinalysis** will be performed only if there is more than a trace amount of blood detected.

9.1.6.4. Stool Sample for Occult Blood

At the screening visit, stool samples will be collected for analysis, if feasible. During the domicile portion of the study, stool samples (if feasible) will be tested once daily (if feasible).

9.1.6.5. Urine Drug Screen

At the screening visit and/or within 3 days prior to Day -1, urine samples will be collected to detect drugs of abuse in adolescents (age 12 to < 18 years). These drugs include, but are not limited to, the following: amphetamines, barbiturates, benzodiazepines, cannabinoids, cocaine, opiates, and urine ethanol. Positive results will exclude the subject from participation with the exception of medications prescribed by the physician during the current hospital stay.

9.1.6.6. Serum Pregnancy Screen

At the screening and within 3 days prior to Day -1 visit, blood samples will be collected and a serum pregnancy test performed for females of childbearing potential only. Positive pregnancy test results will exclude the subject from participation.

9.1.6.7. Low Fat Breakfast or Snack

The single dose of betrixaban will be administered orally with 240 mL water following a low-fat breakfast or snack (e.g., apple sauce, biscuit, fruit, crackers, or commercial nutritional supplement).

- Patient will not have fluids 1 hour prior to dosing.
- Patient will have breakfast or snack.
- Patient will have 240 mL water with dose.
- Patient will not have fluids 1 hour after dosing.
- Patient will wait 2 hours after dosing before ingesting food; there are no post dose restrictions regarding food intake.

For patients enrolled in Part 2 (age 2 to < 12 years old) water intake volumes may differ and will be specified in an amendment to the protocol.

9.2. Adverse and Serious Adverse Events

9.2.1. Definition of Adverse Events

9.2.1.1. Adverse Event

An AE is any undesirable event or any untoward medical occurrence that occurs to a participant during the course of a study, or the protocol-defined time after study termination, whether or not that event is considered study drug-related. A Treatment-Emergent AE (TEAE) is one that occurs following the receipt of any amount of study drug.

Examples of AEs include:

- Any treatment-emergent signs and symptoms (events that are marked by a change from the patient's baseline/entry status [e.g., an increase in severity or frequency of pre-existing abnormality or disorder]).
- All reactions from study drug, abuse of drug, withdrawal phenomena, sensitivity or toxicity to study drug.
- Apparently unrelated illnesses.
- Injuries or accidents.
- Extensions or exacerbations of symptomatology, patient-reported events, new clinically significant abnormalities in clinical laboratory, physiological testing, or physical examination.
- Abnormal laboratory findings considered by the Investigator to be clinically significant, and that represent a worsening from baseline (see also Section 9.2.5.3). An abnormal laboratory value should be recorded as an AE if it:
 - \circ $\,$ Is associated with clinical signs or symptoms,
 - Requires an intervention,
 - Results in a serious adverse event (including the "medically important" criteria), or
 - Results in study termination or interruption/discontinuation of study treatment.

When recording an AE resulting from a laboratory abnormality, the resulting medical condition, if known, rather than the abnormality itself should be recorded (e.g., record "anemia" rather than "low hemoglobin").

When a unifying diagnosis has been made that accounts for several possible signs and/or symptoms, the unifying diagnosis should be selected as the AE term. For example, the combination of general malaise, mild fever, headache, and rhinitis should be described as "upper respiratory syndrome" if this diagnosis has been made, rather than reporting the individual symptoms as separate events.

9.2.1.1.1. Serious Adverse Event

A SAE is an AE occurring during any study phase (i.e., baseline, treatment, washout, or follow-up), and at any dose of the investigational product, comparator, or placebo, that meets any of the following criteria:

• Results in death

• Is immediately life-threatening

Life-threatening means that, in the opinion of the Investigator or Study Sponsor, the patient was at immediate risk of death from the reaction as it occurred, (i.e., it does not include a reaction that hypothetically might have caused death had it occurred in a more severe form).

- Requires in-patient hospitalization or prolongation of existing hospitalization. Hospital admissions and/or surgical operations scheduled to occur during the study period, but planned before the signing of the ICF, are not considered AEs if the illness or disease existed before the patient was enrolled in the trial, provided that it did not deteriorate in an unexpected manner during the trial (e.g., surgery performed earlier than planned).
- Results in persistent or significant disability or incapacity. Disability is defined as a substantial disruption of a person's ability to conduct normal life functions.
- Results in a congenital abnormality or birth defect
- Is an important medical event that may jeopardize the patient or may require medical intervention to prevent one of the outcomes listed above.
 An important medical event is an event that may not result in death, be life-threatening, or require hospitalization but may be considered an SAE when, based upon appropriate medical judgment, it may jeopardize the patient and may require medical or surgical intervention to prevent one of the outcomes listed in the definitions for SAEs. Examples of such medical events include allergic bronchospasm requiring intensive treatment in an emergency room or at home, blood dyscrasias or convulsions that do not result in in-patient hospitalization, or the development of drug dependency or drug abuse.

9.2.1.1.2. Other Adverse Event (OAE)

Not applicable.

9.2.2. Assessing Severity (Intensity) of Adverse Events, Including Serious Adverse Events

Severity (intensity) of each AE will be assessed according to the scale in Table 7:

Table 7: Assessing the Severity (Intensity) of Adverse Events

Classification	Description
Mild	Awareness of sign or symptom, but easily tolerated
Moderate	Discomfort sufficient to cause interference with normal activities
Severe	Incapacitating, with inability to perform normal activities

A distinction should be made between the terms "serious" and "severe" since a SAE is not synonymous with an AE assessed as "severe." The term "severe" is often used to describe the intensity (severity) of a specific event (as in mild, moderate, or severe myocardial infarction); the event itself, however, may be of relatively minor medical significance (such as severe headache). This is not the same as an SAE, which is based on patient/event outcome or action criteria usually associated with events that pose a threat to a patient's life or functioning. A severe AE does not necessarily need to be considered serious. For example, persistent nausea of several hours' duration may be considered severe nausea but not an SAE if the event does not meet the serious criteria. On the other hand, a stroke resulting in only a minor degree of disability may be considered mild, but would be defined as an SAE based on the above noted serious criteria (such as requiring hospitalization). Seriousness (not severity) serves as a guide for defining regulatory reporting obligations.

9.2.3. Assessing Relationship to Study Drug

An Investigator who is qualified in medicine must make the determination of relationship to the investigational product for each AE (Unrelated, Unlikely Related, Possibly Related, or Probably Related). Using the guidelines in Table 8 the Investigator should decide whether, in his or her medical judgment, there is a reasonable possibility that the event may have been caused by the investigational product.

If the relationship between the AE/SAE and the investigational product is determined to be "possible" or "probable" the event will be considered to be related to the investigational product for the purposes of expedited regulatory reporting.

The categories described in Table 8 should be used to assess the causality (i.e., relationship) of AEs to study drug.

Classification	Description
Probable	The AE
	• Follows a reasonable temporal sequence from the time of study drug administration; and/or
	• Follows a known response pattern to the study drug; and
	• Was unlikely to have been produced by other factors, such as the patient's clinical state, therapeutic intervention, or concomitant therapy.
Possible	The AE
	• Follows a reasonable temporal sequence from the time of study drug administration; and/or
	• Follows a known response pattern to the study drug;
	• But could have been produced by other factors, such as the patient's clinical state, therapeutic intervention, or concomitant therapy.
Unlikely	The AE
	• Does not follow a reasonable temporal sequence from the time of study drug administration; and/or
	• Does not follow a known response pattern to the study drug; and
	• Was most likely produced by other factors, such as the patient's clinical state, therapeutic intervention, or concomitant therapy.
Unrelated	This category is applicable to those AEs that are judged to be clearly and incontrovertibly due only to extraneous causes (e.g., the patient's clinical state, therapeutic intervention, or concomitant therapy) and do not meet the criteria for study drug relationship listed under Probable, Possible, or Unlikely.

Table 8: Assessment of Causality of Adverse Events

9.2.4. Recording and Reporting Pregnancy and Outcomes of Pregnancy

Any pregnancy that occurs from the time of enrollment to the last day of follow-up must be recorded on the appropriate page of the eCRF. Pregnancy in itself is not regarded as an AE unless there is a suspicion that an investigational product may have interfered with the effectiveness of a contraceptive medication.

The outcome of any pregnancy (e.g., spontaneous miscarriage, elective termination, normal birth, or congenital abnormality) must be followed up and documented even if the patient was discontinued from the study.

All reports of congenital abnormalities/birth defects are classified as SAEs. Spontaneous miscarriages are also SAEs. Elective abortions without complications are not AEs.

9.2.5. Recording and Reporting Adverse Events, Including Serious Adverse Events, and Abnormal Laboratory Values

9.2.5.1. General Principles

Any AE reported spontaneously by the patient and/or in response to an open question from the study personnel or revealed by observation will be recorded during the study at the investigational site. Please see Section 9.2.5.3 for procedures for recording abnormal laboratory values.

The AE term should be reported in standard medical terminology when possible. For each AE, the investigator will evaluate and report the onset (date and time), resolution (date and time), intensity, causality, action taken, serious outcome (if applicable), and whether or not it caused the patient to discontinue the study. All AEs must be reported on the appropriate page of the eCRF and entered in the clinical database.

9.2.5.2. Reporting Policies for Serious Adverse Events

PPD

If an AE is determined to be serious in nature (i.e., is classified as an SAE), it must be reported on the SAE page of the CRF and reported to the safety team within 24 hours of the investigator becoming aware of the event.

Submit all SAE reports to the Sponsor:

Portola Pharmacovigilance

Contact the Portola Pharmaceuticals, Inc. Medical Monitor for any inclusion/exclusion or study-related questions.

Record all SAEs (related and unrelated) from the signing of the ICF through the last day of follow-up. Any SAE discovered by the Investigator at any time after the study should be reported to the Sponsor Pharmacovigilance contact details above on an SAE form within 1 business day of awareness. The Investigator must complete, sign and date the SAE pages, verify the accuracy of the information recorded on the SAE pages with the corresponding source documents, and submit all SAE reports to Portola Pharmaceuticals, Inc. at the contact information specified above.

Submit additional follow-up information, if required or available, to Portola Pharmaceuticals, Inc. within 1 business day of receipt on a follow-up SAE form and placed with the original SAE information. Record the information on the appropriate section of the CRF and/or study file. Portola Pharmaceuticals, Inc. is responsible for notifying the relevant regulatory authorities of certain events. It is the Principal Investigator's responsibility to notify the IRB or IEC of all SAEs that occur at his or her site. Investigators will also be notified of all unexpected, serious, drug-related events (7/15 Day Safety Reports, also known as SUSARs) that occur at any site during the clinical trial. Each site is responsible for notifying its IRB or IEC of these additional SAEs.

9.2.5.3. Reporting Abnormal Laboratory Tests as Adverse Events

The Investigator will monitor laboratory test findings. If any laboratory test is abnormal during the course of the study, it will be followed up on at the discretion of the Investigator. Abnormal laboratory tests may, in the opinion of the Investigator or the Sponsor, be considered clinically significant and, thus, must be reported as an AE. In such cases, abnormal laboratory test findings must be reported on the AE CRF.

10.0 STATISTICAL CONSIDERATIONS AND DATA ANALYSIS

10.1. Study Design and Objectives

The primary objective of this open-label, multicenter trial in pediatric patients is designed to determine the PK parameters of betrixaban in the pediatric population in several defined age groups: 12 to < 18 years of age and 2 to < 12 years of age. The secondary objectives are to assess the PD activity and safety of betrixaban in the pediatric age categories specified above. The design of the study is summarized in Section 3.1.

10.2. Randomization

No randomization will be needed. In this open-label study, each patient will receive one dose of betrixaban, as defined for each age group.

10.3. General Considerations

No formal hypothesis testing will be performed.

It is anticipated that all statistical analyses will be performed using SAS Version 9.3 (SAS Institute, Inc., Cary, NC, USA) or higher. Additional software may be used for the production of graphics and for statistical methodology not provided by this software package.

A Statistical Analysis Plan (SAP) will be created for this study with complete details and definitions of all planned analyses. The SAP will be finalized prior to database lock.

10.4. Determination of Sample Size

Sample size for each age group is determined by the variance for $AUC_{(0-last)}$ and C_{max} observed from the adult PK studies of betrixaban. The between-subject variability seen in $AUC_{(0-last)}$ as measured by percent coefficient of variation was around 45%. A minimum of 12 subjects are required to target a 90% confidence interval within 60% and 140% of the geometric mean estimates of the $AUC_{(0-last)}$ with at least 80% power.

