3.0 INVESTIGATIONAL PLAN

3.1. Overall Study Design

This is a multiple-center, open-label, study of the PK, PD, and safety of a single dose of betrixaban at up to 80 mg in pediatric patients who meet study entry criteria. To adequately assess PD, any last dose of anticoagulant must not have been taken within one week prior to receiving betrixaban in this study.

Following an up to 30-day screening period, eligible patients who have provided Assent and whose parent or legal guardian has signed an Informed Consent will receive a single, oral dose of betrixaban at 40 mg or 80 mg. The screening visit may be an outpatient visit. Patients will enter (or if hospitalized, remain in) the hospital, clinical research unit, or Phase 1 unit on Day -1, the day before dosing with betrixaban is anticipated, and remain domiciled through 24 hours after betrixaban is administered. They may undergo the remainder of procedures as outpatients, including a Day 7 follow-up safety phone call.

Part 1 (the initial opening of the study) will be conducted in 21 adolescent patients (12 to < 18 years of age) who are assessed to be at risk for VTE but do not require immediate anticoagulation and whose coagulation parameters are normal. Each patient will receive a single, oral, hard gelatin capsule of betrixaban. The dose administered initially to adolescent patients will be 40 mg. After review of the safety data from patients who received 40 mg, additional adolescent patients may be dosed with 80 mg. There will be 2 cohorts of patients in Part 1 of the study. The cohorts are defined as follows:

- Cohort 1 will enroll 3 patients (at least one of each gender), each of whom will receive a single, oral dose of betrixaban at 40 mg in the fed state, and have 10 PK blood sampling time points.
- Cohort 2 will enroll 18 patients (6 patients in each of 3 PK sampling sequences), each of whom will receive a single, oral dose of betrixaban at 80 mg in the fed state, and undergo 5 PK sampling time points.

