## 6.0 STATISTICAL METHODS

### 6.1. General Considerations

After final database lock, all analyses will be performed according to this Statistical Analysis Plan (SAP).

All parameters will be summarized descriptively. No hypothesis tests will be performed. For continuous variables, number of observations, mean, median, standard deviation, and minimum and maximum values, and 95% CI will be presented. For categorical variables, counts, percentages, and 95% CI will be tabulated for each category.

It is anticipated that statistical summaries will be performed using SAS Version 9.4 (SAS Institute, Inc., Cary, NC, USA) or higher. Additional software may be used for the production of graphics and for statistical methodology not available in SAS.

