#### 6.5. Pharmacokinetic Analysis of Betrixaban

#### 6.5.1. **Primary PK Parameters**

The primary PK Parameters are as follows and will be presented per age group by dose, and for individuals, where possible:

- Area under the concentration-time curve to the last measurable concentration above the quantitation limit (AUC(0-last))
- Maximum observed plasma concentration (Cmax)

Summary statistics and listing tables of  $C_{max}$  and AUC will be provided for each age and dose cohort. The subjects who only had 5 time points each will have PK parameters calculated as an average, as it would not be appropriate to assume Cmax or calculate AUC based on the limited time points.

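### The 12 in Protocol 10.4 reproduces, but its precision assumes one AUC per subject, and the planned analysis gives individual AUCs for only 3 of 21 patients

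*Protocol*

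**What the plan says.** Protocol 10.4 sizes each age group on the precision of AUC(0-last): "A minimum of 12 subjects are required to target a 90% confidence interval within 60% and 140% of the geometric mean estimates" of that parameter, "with at least 80% power". The variability input is a between-subject CV of about 45%, "observed from the adult PK studies of betrixaban". No formula is named, and no CV is given for Cmax, the other primary parameter. Protocol 10.3 adds "No formal hypothesis testing will be performed", so precision is the whole basis for the number.

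Protocol 3.1 gives rich sampling (10 times) to the 3 patients of Cohort 1 at 40 mg, and 5 times per patient to the 18 patients of Cohort 2 at 80 mg, six in each of three sequences. Protocol 10.6 derives the PK parameters by age group with population PK, and individually only where sampling is rich. SAP 6.5.1 gives the five-point patients an averaged result because "it would not be appropriate to assume Cmax or calculate AUC based on the limited time points".

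On reporting, the protocol synopsis (Statistical Methods) specifies the geometric mean with a 90% CI. SAP 6.1 lists, for continuous variables, the number of observations, mean, median, standard deviation, "minimum and maximum values, and 95% CI will be presented". SAP 6.5.1 asks only for summary statistics and listings. SAP 6.11 records the loss of Part 2 and of the PD measurements, and no change to the PK summaries.

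**The concern.** A sample size built on between-subject variance describes the mean of n individual AUCs. If most patients have no individual AUC, the stated precision belongs to an analysis that will not be done. Protocol 10.4 is the only quantitative justification for the number of children enrolled, and AUC(0-last) is a primary parameter. A reader of the final report could credit the exposure estimates with a precision that was never worked out for them. The interval that would show the actual precision is not among the SAP's listed statistics.

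**Working it through.** **Inputs.** From Protocol 10.4: CV 45%, 90% two-sided CI, limits 60% and 140%, power 80%, n = 12. On the log scale, σ = √ln(1 + 0.45²) = 0.4294. The limits are ln 0.6 = −0.511 and ln 1.4 = 0.336, so the upper limit is the tighter one. The 90% interval is the log mean ± h, with h = t(0.95, n−1)·s/√n.

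**1. Reproducing the 12.** Protocol 10.4 does not say what the limits are relative to, so two criteria were tried.

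- Whole interval: both ends must lie within 60% to 140% of the true geometric mean, with mean and SD both random.
- Half-width: the interval need only be narrow enough around its own estimate, h ≤ ln 1.4, with only the SD random. The probability is P(χ² with n−1 df ≤ (n−1)·n·(ln 1.4)²/(t²σ²)).

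| n | Whole interval | Half-width |
|---|---|---|
| 3 | 11.7% | 19.4% |
| 8 | 55.7% | 78.6% |
| 9 | 63.8% | 88.0% |
| 11 | 75.8% | 97.6% |
| 12 | 80.1% | 99.1% |
| 13 | 83.7% | 99.7% |

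Under the whole-interval criterion, 12 is exactly the smallest n that reaches 80%. It is slightly sensitive to method: with 0.45 used directly as the log SD, or with ±40% on the arithmetic scale, 12 gives 76.2% or 78.4%, and 13 is needed.

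**2. What the calculation needs against what the analysis supplies.** It needs at least 12 individual AUC(0-last) values. Under Protocol 10.6 and SAP 6.5.1, Cohort 1 supplies 3 and Cohort 2 supplies none.

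**3. Precision in Cohort 1.** With n = 3, t(0.95, 2) = 2.920, so h = 2.920 × 0.4294/√3 = 0.724. Then exp(±0.724) gives 48% to 206% of the geometric mean, against a target of 60% to 140%. For comparison, at n = 12, h = 1.796 × 0.4294/√12 = 0.223, giving 80% to 125%. Both intervals fix the observed log SD at 0.4294. With three patients the observed SD will vary widely. The probability of meeting the target is 11.7% (whole interval) or 19.4% (half-width).

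**4. Precision in Cohort 2.** If 18 individual AUCs existed, the interval would be exp(±1.740 × 0.4294/√18), or 84% to 119%. They are not planned. From the sequences in Protocol Figure 1, the mean concentration at each post-dose time rests on:

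- 6 patients at 0.5, 1, 4 and 120 hours;
- 12 patients at 2, 3, 12 and 24 hours.

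No post-dose time has all 18. Only Sequence A is sampled at 120 hours, while B and C end at 24 hours, so the last sampling time differs between patients. The uncertainty of an AUC built from such a profile depends on these counts and on the correlation of samples within a patient. Neither enters the calculation in 10.4, and neither document gives a method for the interval.

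**5. The reported interval.** The study was sized on a 90% interval for a geometric mean. SAP 6.1 lists a mean with a 95% interval. The change of level alone matters: under the whole-interval criterion with a 95% CI, 12 gives 65.9% and 16 would be needed.

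**6. Level of derivation.** The synopsis (Statistical Methods) and the opening of Protocol 2.3 have the parameters determined patient by patient. Protocol 10.6 and SAP 6.5.1 do not, and 2.3.1 itself puts AUC(0-last) at age-group level except where sampling is rich.

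**The case against.** Five points can be made for the plan.

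- **The arithmetic.** A reader might infer from the half-width column that 9 subjects suffice and that 12 is an error. The documents do not support that. The wording of 10.4 permits the half-width reading but does not require it; the whole-interval criterion returns 12 exactly, and 12 satisfies both. Writing 9 into the protocol would give 63.8% under the criterion that reproduces the stated figure. This point stands in full.
- **The target is per age group.** Protocol 10.4 does not promise the precision for Cohort 1 alone, and the adolescent group has 21 patients. That is correct, but the 21 span two doses. Protocol 1.0 reports roughly a threefold rise in adult steady-state exposure when the dose was doubled from 40 to 80 mg, and SAP 6.5.1 presents results by dose. The 21 are not one sample of AUCs.
- **Population PK can give an interval.** A reader might infer that this design offers no precision at all. That is too strong: a population model or pooled profile from 18 patients can carry a confidence interval. Its width just does not follow from 10.4 and is stated nowhere.
- **The synopsis still specifies the geometric mean and 90% CI.** True, and SAP 6.1 is a general rule that does not forbid them. But SAP 6.1 also says that analyses after database lock follow the SAP, which never mentions either statistic.
- **Low stakes.** No hypothesis is tested, Part 2 was cancelled and development has stopped. This limits the consequence to how the primary PK results are read.

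**Conclusion.** The sample-size figure stands. What fails is the link from it to the analysis: a precision derived for at least 12 individual AUCs is stated for a design whose planned analysis yields 3, at one dose, and an average from 18 at another. For the 3, the chance of meeting the target is 12% to 19%. For the 18, the precision is unstated, not absent. The statistic on which the study was sized also drops out between the protocol synopsis and the SAP without being recorded as a change.

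This rests on log-normal AUCs, on the adult CV of 45% holding in adolescents, and, for the 48% to 206% interval, on an observed log SD of 0.429. No CV is given for Cmax, so its precision cannot be checked.

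**What to change.** 1. In Protocol 10.4, keep 12 and name the criterion: at least 80% probability that the whole 90% CI lies within 60% to 140% of the true geometric mean, at CV 45%.
2. State there that this precision applies only where individual or model-based individual AUCs exist, and that it does not hold for the 3-patient 40 mg cohort. As Part 1 has already been run, items 1 and 2 could instead be recorded in SAP 6.11.
3. In SAP 6.5.1, add the geometric mean and 90% CI for AUC(0-last) and Cmax. Take the interval for the pooled Cohort 2 estimate from the population PK model, or from a bootstrap that resamples patients within sequence.
4. Reconcile the patient-level wording in the synopsis (Statistical Methods) and Protocol 2.3 with Protocol 10.6 and SAP 6.5.1.

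The cost is wording, one added pair of summary statistics and a little more analysis work. The stated precision for Cohort 1 becomes less favourable. Enrolment does not change.
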